9.4 Hormonal Test

9.4.1 Analysis Set

Analysis will be performed in SAF.

9.4.2 Analysis Items and Data Handling

1) Analysis Items

Thyroid-stimulating hormone (TSH), free triiodothyronine (free T3), and free thyroxine (free T4).

2) Data Handling

Data will be analyzed as observed without imputing missing data.

Any hormonal test values that fall below the detection or quantification limit will be imputed to be the detection or quantification limit.

9.4.3 Analysis Methods

The analysis results will be summarized by dose level groups separately and totality.

- 1) Summary statistics (no. of subjects, mean, standard deviation, median, minimum, and maximum) will be provided for each Hormonal test parameter by the time of measurement.

9.5 Vital Signs

9.5.1 Analysis Set

Analysis will be performed in SAF.

9.5.2 Analysis Items and Data Handling

- 1) Analysis Items

Systolic blood pressure/diastolic blood pressure, pulse rate, temperature, weight, and percutaneous oxygen saturation as measured using pulse oximetry (SpO₂).

- 2) Data Handling

Data will be analyzed as observed without imputing missing data.

Any vital sign parameter values that fall below the detection or quantification limit will be imputed to be the detection or quantification limit.

9.5.3 Analysis Methods

The analysis results will be summarized by dose level groups separately and totality.

Summary statistics (no. of subjects, mean, standard deviation, median, minimum, and maximum) will be provided for each vital sign parameter by the time of measurement.

9.6 12-lead ECG

9.6.1 Analysis Set

Analysis will be performed in SAF.

9.6.2 Analysis Items and Data Handling

- 1) Analysis Items

Heart rate, RR interval, QT interval, QTcF, PR interval, QRS complex.

2) Data Handling

12-lead ECG data will be analyzed as observed without imputing missing data.

Any 12-lead ECG parameter values that fall below the detection or quantification limit will be imputed to be the detection or quantification limit.

QTcF will be calculated using the following compensation formula.

$$\text{QTcF (ms)} = \text{QT interval} / (\text{RR interval})^{1/3}.$$

9.6.3 Analysis Methods

The analysis results will be summarized by dose level groups separately and totality.

- 1) For 12-lead ECG parameters (observed values of RR interval, QT interval, Fridericia's corrected QT interval [QTcF], QRS complex, and PR interval, and their changes [ΔQTcF , ΔQRS , and ΔPR]), observed value (HR) and change (ΔHR) of heart rate, summary statistics and frequency distribution for each category will be summarized at each time point.
- 2) For maximum QTcF, maximum ΔQTcF , maximum QRS, maximum PR, and maximum heart rate of subjects, frequency distribution for each category will be calculated.

Item	Classification
RR (ms) (observed value)	≤ 600 , > 600 – 1200 , > 1200
P-R (ms) (observed value)	≤ 120 , > 120 – 200 , > 200
QRS (ms) (observed value)	≤ 60 , > 60 – 109 , > 109
Heart rate (observed value)	≤ 50 , > 50 – 100 , > 100
QT interval, ΔQTcF (ms) (observed value)	≤ 450 , > 450 – 480 > 480 – 500 , > 500
ΔQTcF (ms) (change)	≤ 30 , > 30 – 60 , > 60

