3.2.3 Subject Exclusion Criteria

Patients satisfying any of the following criteria will be excluded:

1. Current or prior severe hypersensitivity to another antibody product
2. Adverse drug reactions due to prior treatments or remaining effects of surgical therapy that, in the principal or sub investigator's opinion, may interfere with the evaluation of the investigational product
3. Active autoimmune disease or history of chronic or recurring autoimmune disease (Appendix 3).
4. Current or prior interstitial lung disease or pulmonary fibrosis diagnosed based on diagnostic imaging or clinical findings.
5. Active diverticulitis or symptomatic gastrointestinal ulcerative disease
6. Multiple primary cancers (except for completely resected basal cell cancer, stage I squamous cell carcinoma, carcinoma in situ, intramucosal carcinoma, or superficial bladder cancer or any other cancer from which the patient has been recurrence-free for at least 5 years)
7. Original cancer or metastases to the brain or meninges (unless such lesions are asymptomatic and do not require treatment)
8. Pericardial effusion, pleural effusion, or ascites requiring treatment
9. Cancer pain not stable with a fixed regimen of an analgesic
10. History of transient ischemic attack, cerebrovascular accident, thrombosis, or thromboembolism

(pulmonary arterial embolism or deep vein thrombosis) within 180 days of enrollment.

11. Any of the following cardiovascular diseases that are uncontrollable or severe:
 - Myocardial infarction within 180 days of enrollment
 - Uncontrollable angina pectoris within 180 days of enrollment
 - New York Heart Association (NYHA) Grade III or IV congestive cardiac failure
 - Hypertension (systolic blood pressure \geq 150 mmHg or diastolic blood pressure \geq 90 mmHg persisting for \geq 24 hours) despite appropriate treatment
 - Arrhythmia requiring treatment
12. On anticoagulant therapy (other than antiplatelet therapy with low-dose aspirin) or having a disease requiring anticoagulant therapy.
13. A serious concomitant disease such as liver failure, renal failure or uncontrollable diabetes.
14. Patients requiring transplantation or with a history of transplantation except autotransplantation
15. Has received a systemic corticosteroid (unless temporarily for testing, prophylaxis, or a similar purpose unrelated to an autoimmune disease) or an immune suppressant 28 or fewer days before enrollment.

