3.7 Sample size determination

3.7.1 Planned Number of Subjects

Total 18 subjects (6 subjects in each group)

Rationale

ONO-4538 is a fully human IgG4 monoclonal antibody and it is reported that there is no great distinction between Japanese and non-Japanese regarding the pharmacokinetics of monoclonal antibody. Therefore the sample size which the pharmacokinetics can be evaluated is set at 6 subjects in each group in this study.

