4.3 Criteria for Handling Evaluation Time Points

If the actual date of examination is not the protocol-specified date of examination, the examination data will be accepted, only when they are measured within the following criteria. If multiple data are present within the time window of a given time point, data which are obtained at a time point nearest the specified timing of examination will be preferred. If multiple safety data are obtained before and after the specified date and the lengths of time from the specified date and time are identical, those obtained after the specified date and time will be preferred.

1. Treatment Period

Item	Treatment period						
	1			2,3,4	8	15	22
Trial day	Before administration ^{a)}	After the start of the administration	After the end of the administration				
		1 hr	2 hr	8 hr			
Time window (days)	1	± 10 min	± 15 min	± 30 min	1	-2 - +2	-3 - +3
						-3 - +3	

a) Performance Status and laboratory test results which have been obtained within seven days before enrollment will be accepted.

2. Post-treatment Follow-up Period (subjects who have terminated the treatment period)

Item	At Discontinuation	Follow-up during 28 days after the discontinuation or 22 days only if the subjects will not join ONO-4538-14
Trial day		
Time window (days)	+3	-7 - +7

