9.1.2 Analysis Items and Data Handling

1) Analysis Items

- (1) Overall adverse events, adverse drug reactions and number of deaths.
- (2) Classification of adverse events

2) Data Handling

An adverse event is any unfavorable or unintended sign (including an abnormal laboratory finding), symptom or disease during a clinical trial, whether or not related to the investigational product. Of note, tabulation will include adverse events whose symptoms have occurred/worsened during the period from the first dose of the study drug until 28 days after the discontinuation or Day 22 only if subjects will not join the ONO-4538-14 study (or until the start of subsequent anti-cancer therapy, whichever comes first). In addition, all adverse events that occur during the treatment period or the post-treatment follow-up period will be listed and reported.

All adverse events reported in this clinical study will be coded by SOC (System Organ Class) and PT (Preferred Term) using MedDRA (Current version). Treatment-emergent adverse events are those events that occur or worsen on or after the first dose of study treatment up until end of study treatment.

For the analysis of adverse events, only treatment-emergent adverse events (TEAEs) will be included in the summary tables.

In case the same adverse events in terms of SOC and PT occurs to one subject more than once, it will be considered as a single event, and the highest severity and relationship status among all events will be taken into account.

Severity of adverse events will be classified using NCI-CTCAE, and where NCI-CTCAE is inapplicable, it will be classified as grade 1 ('Mild'), grade 2 ('Moderate'), grade 3 ('Severe'), grade 4 ('Life-threatening or disabling') or grade 5 ('Death') based on the maximum intensity. With respect to the relationship to study drug, 'Related' will be regarded as related, and 'Not related' will be regarded as unrelated.

- (1) Number of deaths

The number of deaths will be defined as the total number of subjects who have died during the period from the first dose of the study drug until 28 days after the discontinuation or 22 days only if subjects will not join the 4538-14 study (or until the start of subsequent anti-cancer therapy, whichever comes first).

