10.2 Significance Level to Be Used

No significance level is defined because no tests will be performed.

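### The per-subject maximum ECG tables (SAP 9.6.3, item 2) cannot separate subjects who newly passed a limit after dosing from those already above it

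*SAP*

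**What the plan says.** SAP 9.6.3 has two items for the 12-lead ECG.

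- Item 1 covers observed RR, QT, QTcF, QRS, PR and heart rate, and changes in QTcF, QRS, PR and heart rate. For these, "summary statistics and frequency distribution for each category will be summarized at each time point".
- Item 2 works per subject. It covers maximum QTcF, maximum change in QTcF, "maximum QRS, maximum PR, and maximum heart rate of subjects, frequency distribution for each category will be calculated". The upper limits in the class table are 200 ms for PR, 109 ms for QRS, 100 for heart rate, and 450, 480 and 500 ms in the QT row. That row is labelled as QT interval and ΔQTcF (observed value); I take it to apply to observed QTcF.

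No other section says which ECGs enter a maximum. The data handling in 9.6.2 begins "12-lead ECG data will be analyzed as observed without imputing missing data" and goes on to detection limits and the QTcF formula. It defines neither a baseline nor a post-dose window. Section 4.3 has a rule that starts "If multiple data are present within the time window of a given time point"; it chooses one value per time point and removes no time point. The schedule (SAP Table 3) includes ECGs at screening and on Day 1 before administration.

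**The concern.** In an uncontrolled study the subject's own pre-dose ECG is the natural reference for an abnormal ECG after dosing. Item 2 does not use it for the absolute values. Taken literally, a screening value can even set a subject's class. On the more generous reading, in which only post-dose ECGs count, a long-standing abnormality still shares a cell with a new one.

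The SAP applies the principle elsewhere: "Treatment-emergent adverse events are those events that occur or worsen on or after the first dose of study treatment". The ECG tables have no counterpart. Eligibility does not remove the problem, because the one ECG-related exclusion is "Arrhythmia requiring treatment", and no limit is set for QTcF, PR, QRS or heart rate.

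At stake is how a listed safety endpoint can be read. The SAP says "No significance level is defined because no tests will be performed", so the descriptive tables are themselves the ECG result.

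**Working it through.** The plan states no ECG rate, so there is no figure to reproduce. All percentages below are illustrations under assumed inputs.

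**Step 1: weight of one subject.** SAP 3.7.1 plans 6 subjects per group and 18 in all. One subject is 1/6 = 16.7% of a group and 1/18 = 5.6% of the total.

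**Step 2: chance of meeting the problem.** Let p be the share of subjects above a given limit before dosing (assumed). The chance of at least one such subject among n is 1 − (1 − p)^n.

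| p | at least one of 6 | at least one of 18 | expected in 18 (18p) |
|---|---|---|---|
| 2% | 11.4% | 30.5% | 0.4 |
| 5% | 26.5% | 60.3% | 0.9 |
| 10% | 46.9% | 85.0% | 1.8 |
| 20% | 73.8% | 98.2% | 3.6 |

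**Step 3: simulation with no drug effect.** There were 400,000 subjects, each with 2 pre-dose and 10 post-dose ECGs. Each value is a subject mean plus independent normal error. The 2 + 10 split follows the 12 marks in the ECG row of Table 3. That table is broken in the text available, so the 10 is an assumption. Columns give the percentage of subjects above the limit: (a) maximum over all ECGs; (b) maximum over post-dose ECGs; (c) post-dose maximum above the limit with neither pre-dose ECG above it.

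| Measure, limit | mean; between-subject SD; within-subject SD | (a) | (b) | (c) |
|---|---|---|---|---|
| PR >200 | 160; 20; 8 | 9.32 | 8.79 | 4.78 |
| QRS >109 | 92; 9; 4 | 12.96 | 12.19 | 6.74 |
| Heart rate >100 | 75; 10; 8 | 13.81 | 12.52 | 9.36 |
| QTcF >450 | 415; 18; 10 | 16.06 | 14.98 | 9.12 |

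- *Effect of the post-dose restriction alone, (a) − (b):* 0.53, 0.77, 1.29 and 1.08 percentage points. Multiplied by 18, that is 0.10, 0.14, 0.23 and 0.19 of a subject.
- *Already above on a pre-dose ECG, (a) − (c):* 4.54, 6.22, 4.45 and 6.94%. As a share of (a), this is 49%, 48%, 32% and 43%. In 18 subjects it is 0.8, 1.1, 0.8 and 1.2 subjects.
- *The same among those counted post-dose, ((b) − (c))/(b):* 46%, 45%, 25% and 39%.
- *Pre-dose class from the Day 1 ECG only, same simulation:* 32%, 31%, 15% and 26% of those in (b). The share falls because one pre-dose ECG catches fewer high values than two.

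**Step 4: other inputs.** A second set took QTcF mean 420 to 430 (SDs 15 and 8 to 12), PR 160 (20 and 6) and heart rate 78 (11 and 7). On the definition used for (a) − (c), the share already above was 38% to 55%.

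**The case against.** The strongest reply is that the SAP already gives most of what is needed.

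- Item 1 counts subjects per class at every time point, so it shows how many were above each limit before dosing. A reader might infer that item 2 is the only count of abnormal ECGs; that is not so. But item 1 counts at group level. It cannot show whether the subject above a limit before dosing is the one above it later.
- Item 1 also summarises changes in QTcF, QRS, PR and heart rate, and item 2 classifies the maximum change in QTcF. For QTcF this is a real per-subject comparison, although its baseline is not defined. QRS, PR and heart rate have no per-subject maximum change.
- Adverse events are limited to onset or worsening after the first dose, and section 10.3 foresees display of individual data. With 18 subjects, a reader could match values by hand. This lowers the stakes but does not make the planned table answer the question.
- The SAP is silent on pre-dose ECGs rather than explicit in including them. This stands, and Step 3 shows that little turns on it.

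Two stronger readings should be set aside. With 2 of 12 ECGs before dosing, one might infer that 17% of subjects (3 of 18) are misclassified. That is how often the maximum would fall on a pre-dose ECG by chance. It is not how often the class would change. Nor does the SAP attribute pre-existing abnormalities to the drug; that would be a reader's inference from the table.

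**Conclusion.** The point holds as a weakness in a descriptive safety table. For QTcF, QRS, PR and heart rate, item 2 mixes pre-existing and new values above a limit, on either reading of which ECGs enter the maximum. The gap is clearest for QRS, PR and heart rate, where no per-subject change is tabulated.

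The size is illustrative only. Roughly one third to one half of counted subjects would already be above the limit on a pre-dose ECG, and fewer if Day 1 alone defines the pre-dose class. In this trial that is about one subject per measure under the inputs tabulated in Step 3. The means, SDs and number of post-dose ECGs are all assumed. What needs no assumption is that one subject moves a dose-group rate by 16.7 percentage points.

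The pharmacokinetic objective and the sample size are not affected, and the plan contains no test that could be.

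**What to change.** In SAP 9.6.3, item 2:

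1. Define each maximum as the maximum over ECGs recorded after the start of ONO-4538 administration.
2. For QTcF, QRS, PR and heart rate, cross-tabulate the class of that maximum against the class of the Day 1 pre-dose ECG, by dose group and in total. The number newly above each limit can then be read directly.

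The second change is essential; the first alone would leave the tables almost as they are. It would be consistent to name the same Day 1 ECG as the baseline for the change values.

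The cost is one phrase and one small table from data already collected.

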10 GENERAL PRESENTATION OF SUMMARIES AND ANALYSES

10.1 Summary Statistics

As summary statistics, mean, standard deviation, median, maximum, and minimum will be calculated unless otherwise noted.

10.2 Significance Level to Be Used

No significance level is defined because no tests will be performed.

10.3 Decimals

When displaying the individual data, the number of significant figures will be as shown below. For the mean, standard deviation, and median, the number of significant figures will be the number of significant figures for the individual data + 1. For example, if the number of significant decimal places for individual items of data is 1, that for the mean, standard deviation, and median will be 2.

- Background factors and efficacy endpoint

Integer value (No decimal places)	One decimal place
Time from diagnosis date of primary cancer to first dose date of the investigational product (days)	Height (cm)
Age (years)	Weight (kg) BMI (kg/m ²)

· Laboratory values

Integer value (Figures after the decimal point will not be displayed.)	One decimal place
White blood cell count (/mm ³)	MCH (pg)
Red blood cell count (10 ⁴ /mm ³)	MCHC (%)
MCV (fL)	Hemoglobin (g/dL)
AST (GOT) (U/L)	Hematocrit (%)
ALT (GPT) (U/L)	Platelet count (10 ⁴ /mm ³)
ALP (U/L)	Albumin (g/dL)
γ-GTP (U/L)	Total protein (g/dL)
LDH (U/L)	Total bilirubin (mg/dL)
CK (CPK) (U/L)	Direct bilirubin (mg/dL)
Blood glucose (mg/dL)	Uric acid (mg/dL)
BUN (mg/dL)	K (mEq/L)
Na (mEq/L)	Ca (mEq/L)
Cl (mEq/L)	P (mEq/L)
Neutrophil (/mm ³)	CRP (mg/dL)
Lymphocyte (/mm ³)	SP-D (ng/mL)
Eosinophil (/mm ³)	
Basophil (/mm ³)	
Monocyte (/mm ³)	
RA (IU/mL)	
KL-6 (U/mL)	
Two decimal places	Three decimal places
Creatinine (mg/dL)	Urine specific gravity
Free triiodothyronine (pg/mL)	Thyroid-stimulating hormone (μIU/mL)
Free thyroxine (ng/dL)	

· Vital signs

Integer value (No decimal places)	One decimal place
Systolic blood pressure (mmHg)	Temperature (°C)
Diastolic blood pressure (mmHg)	SpO ₂ (%)
Pulse rate (bpm)	
Respiratory rate (beats/min)	

- 12-lead ECG

Integer value (No decimal places)
Heart rate (beats/min)
RR interval (ms)
QT interval (ms)
QTcF (ms)
PR interval (ms)
QRS complex (ms)

10.4 Site Pooling Method

NA

10.5 Software for Statistical Analysis

To display analysis, tabulation, and part of figures and tables, SAS Ver. 9.3 or higher, SAS institute, Cary, NC, USA will be used.

For lists, figures, and tables, Microsoft Word will be used.

11 INTERIM ANALYSIS

No interim analysis will be performed

12 DATA REVIEW

12.1 Objectives

After data collection, a preliminary inspection will be performed using unlocked data to examine whether to accept data and subjects, possible variable transformation, definitions of outliers, classification by stratification factors, and others and thereby to decide an appropriate analysis method compatible with data.

12.2 Analysis Set

Analysis will be performed in subjects receiving the study drug.

12.3 Analysis Items and Data Handling

- 1) Analysis Items
 - (1) Background Demographic factors
 - (2) Summary of TEAE and Incidence of TEAEs by SOC and PT
- 2) Data Handling

All items will be handled as defined previously in the analysis policy.

12.4 Analysis Methods

The analysis results will be summarized by dose level groups separately and totality.

- 1) Summary statistics and frequency distribution of background factors will be calculated, and classification will be decided.
- 2) Incidences of adverse events will be calculated. In addition, incidences of adverse events by SOC and PT will be summarized according to Grade.

The above analyses included a total of 18 subjects for whom data entry was completed as of Dec 17, 2014.

13 CHANGE FROM PROTOCOL

1) [4.1 Definitions of Groups](#) 1) Enrolled Set (ENR)

(1) Content of change

The Enrolled Set (ENR) was added.

(2) Reason for change

The Enrolled Set (ENR) will be evaluated for subject without administration as an analysis population.

2) [8.2 Analysis Items and Data Handling](#) 1) Background Factors

(1) Content of change

Tumor diameter of target lesion was deleted.

(2) Reason for change

As part of the efficacy analysis in the ONO-4538-14, analysis of the development of tumor diameter and evaluation of baseline characteristics will be performed using data of ONO-4538-14 study incorporated with data of this study.

14 SAS PROCEDURE FOR ANALYSIS

NA

15 REFERENCES

NA

Addendum 1 List of Select Adverse Events

Category	Preferred Term
Endocrine Adverse Events	Adrenal insufficiency Adrenal suppression Blood corticotrophin decreased Blood corticotrophin increased Hypothalamic pituitary adrenal axis suppression Secondary adrenocortical insufficiency Diabetes mellitus Latent autoimmune diabetes in adults Hypophysitis Autoimmune thyroiditis Blood thyroid stimulating hormone decreased Blood thyroid stimulating hormone increased Hyperthyroidism Hypothyroidism Thyroid function test abnormal Thyroiditis Thyroiditis acute Thyroxine decreased Thyroxine free decreased Thyroxine free increased Thyroxine increased Tri-iodothyronine uptake increased
Hypersensitivity/Infusion Reactions	Anaphylactic reaction Anaphylactic shock Bronchospasm Hypersensitivity Infusion related reaction
Gastrointestinal Adverse Events	Colitis Colitis ulcerative Diarrhoea Enteritis Enterocolitis Frequent bowel movements Gastrointestinal perforation

Hepatic Adverse Events	Acute hepatic failure Alanine aminotransferase increased Aspartate aminotransferase increased Bilirubin conjugated increased Blood bilirubin increased Drug-induced liver injury Gamma-glutamyltransferase increased Hepatic enzyme increased Hepatic failure Hepatitis Hepatitis acute Hyperbilirubinaemia Liver disorder Liver function test abnormal Liver injury Transaminases increased
Pulmonary Adverse Events	Acute respiratory distress syndrome Acute respiratory failure Interstitial lung disease Lung infiltration Pneumonitis
Renal Adverse Events	Blood creatinine increased Blood urea increased Creatinine renal clearance decreased Hypercreatininaemia Nephritis Nephritis allergic Nephritis autoimmune Renal failure Renal failure acute Renal tubular necrosis Tubulointerstitial nephritis Urine output decreased
Skin Adverse Events	Blister Dermatitis Dermatitis exfoliative Drug eruption

	Eczema
	Erythema
	Erythema multiforme
	Exfoliative rash
	Palmar-plantar erythrodysaesthesia syndrome
	Photosensitivity reaction
	Pruritus
	Pruritus allergic
	Pruritus generalised
	Psoriasis
	Rash
	Rash erythematous
	Rash generalised
	Rash macular
	Rash maculo-papular
	Rash papular
	Rash pruritic
	Skin exfoliation
	Skin hypopigmentation
	Skin irritation
	Stevens-Johnson syndrome
	Toxic epidermal necrolysis
	Urticaria
	Vitiligo

MedDRA version 17.1
